Further tumor imaging will be performed in all patients every 9 weeks for the first 46 weeks and then 12-weekly thereafter until progression (which may be confirmed). On each occasion, tumor assessments will include imaging of the chest, abdomen and pelvis. Additional anatomy, including brain and bone, should be imaged based on signs and symptoms of individual patients. Disease response will be evaluated at these time points according to RECIST 1.1. If either or both of the study treatments are stopped for any reason other than confirmed progression, tumor imaging will continue every 12 weeks until confirmed progression.

Patients who are suspected of having a complete or partial response will have their response confirmed at the next scheduled assessment or no earlier than 4 weeks (28 days) later.

Blood sampling for PBMC and Axl signaling and inhibition biomarker analysis will be performed at Screening, Cycle 1, Days 4 and 8 and every study visit thereafter until Cycle 9, Day 1.

Blood sampling for BGB324 pharmacokinetic (PK) analysis will be performed on blood samples taken on:

- Cycle 1, Days 1 and 3 as follows: pre-dose and at 2, 4, 6 and 8 hours post dose;
- Cycle 1, pre-dose on Days 2, 4, 8 and 15;
- Cycles 2 and 3, pre-dose (study days 22 and 43 respectively).

Blood sampling for future pembrolizumab PK analysis will be performed on blood samples taken pre-dose on Cycle 1, Days 1 to 4, 8 and 15 and then pre-dose at Cycles 2 and 3 (study days

22 and 43 respectively). These samples will be frozen and stored centrally for future reference and analysis.

Patients with tumor amenable to repeat sampling may have additional fresh biopsies taken on up to 2 occasions post-dose at time points agreed between the Investigator and the patient. Where possible, efforts will be made to obtain follow up biopsy material where a patient has responded to treatment or has progressed on treatment.

Further details on sample collection and handling for all PK and biomarker assessments are described in the Laboratory Manual.

Patients who discontinue BGB324 treatment (for reasons other than disease progression) may be able to continue with (monotherapy) pembrolizumab until 106 weeks (that is, 35 completed cycles of pembrolizumab). These patients will no longer be required to have the following assessments from 6 weeks after the discontinuation of BGB324 (unless clinically indicated):

- ECG;
- Echocardiogram (or Multi Gated Acquisition Scan (MUGA));

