- 8 Fresh tumor tissue from all patients at Screening is mandatory, and optional at up to 2 time points during participation in the clinical trial ('on-study' biopsy). Where possible, these optional samples should be taken at the point of tumor response or progression. Suitable archival biopsy material may also be obtained at Screening. Please refer to protocol [Section 5.3.13](#), the Laboratory or Pathology Manual for full details on biopsy sample collection, time-points, processing, storage and shipment. If a patient discontinues BGB324 (but continues pembrolizumab), there is no requirement for the optional 'on study' biopsy.
- 9 Blood samples will be collected at Screening (or D1 pre-dose), D4, D8, then at every study visit up to and including C9 D1 to prepare PBMC and serum samples for Axl signaling and inhibition biomarker assessment. Please refer to the Laboratory Manual for full details on biomarker sample collection, time-points, processing, storage and shipment. If a patient discontinues BGB324 (but continues pembrolizumab), there is no requirement for biomarker blood samples.
- 10 Pembrolizumab dose of 200 mg will be administered every 3 weeks (timing window +/- 3 days). Each dose will be infused over 30 minutes (timing window -5/+10 minutes)
- 11 BGB324 will be taken orally once daily. On visits when pembrolizumab and BGB324 are given on the same day, pembrolizumab must be given first and the patient observed for 1 h prior to administration of BGB324.
- 12 a) The maximum PK sampling time points for the measurement of BGB324 in blood will be: C1 D1 pre-dose, 2, 4, 6, 8 hours ; D2 pre-dose; D3 pre-dose, 2, 4, 6, 8 hours; D4 pre-dose; and then pre-dose at C1D8, C1D15, C2D1 and then C3D1. Samples should be taken contemporaneously with the ECG assessments on C1 D1-4. All sample times are approximate but every effort must be made to take PK samples at specified times.

- b) The maximum PK sampling time points for the measurement of pembrolizumab in blood will be: C1 D1 pre-dose; D2; D3; D4; and then at C1D8, C1D15; C2D1 pre-pembro dose and then C3D1 pre-pembro dose. All sample times are approximate but every effort must be made to take PK samples at specified times

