8. Current treatment with any agent known to cause Torsade de Points which cannot be discontinued at least five half-lives or two weeks prior to the first dose of study treatment.
9. Screening 12-lead ECG with a measurable QTc interval according to Fridericia's correction  $>$ 450 ms.
10. Is currently participating and receiving study therapy or has participated in a study of an investigational agent and received study therapy or used an investigational device within 4 weeks of the first dose of study treatment.
11. Has had prior chemotherapy, targeted small molecule therapy, or radiation therapy within 2 weeks prior to study Day 1 or who has not recovered (i.e.,  $\leq$  Grade 1 or at baseline) from AEs due to a previously administered agent. *Note: Subjects with  $\leq$  Grade 2 alopecia are an exception to this criterion and may qualify for the study.*
12. Received an anti-cancer monoclonal antibody (mAb) within 4 weeks prior to the first dose of study treatment or who has not recovered (i.e.  $\leq$ Grade 1 or baseline) from AEs due to agents administered more than 4 weeks earlier.
13. Major surgery within 28 days prior to start of study treatment and failure to have recovered adequately from the toxicity and/or complications from the intervention prior to the first dose of study treatment. *Note: Major surgery does not include procedures for insertion of venous catheters or biopsies.*
14. Received transfusion of blood products (including platelets or red blood cells) or administration of colony stimulating factors (including G-CSF, GM-CSF or recombinant erythropoietin) within 4 weeks prior to the first dose of study treatment. *Note: Patients receiving stable dose of growth factors with a hemoglobin value that meets Inclusion Criterion 10b may be included.*

15. Has a diagnosis of immunodeficiency or is receiving systemic steroid therapy or any other form of immunosuppressive therapy within 7 days prior to the first dose of study treatment.
16. Active autoimmune disease that has required systemic treatment in past 2 years (i.e. with use of disease modifying agents, corticosteroids or immunosuppressive drugs).  
*Note: Replacement therapy (e.g. thyroxine, insulin, or physiologic corticosteroid replacement therapy for adrenal or pituitary insufficiency, etc.) is not considered a form of systemic treatment.*
17. Known history of human immunodeficiency virus (HIV 1/2 antibodies).

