##### Screening (up to 28 days prior to Day 1)

- ~ Demographics – gender, ethnicity, race, age (birth month and year)
- ~ Medical history
- ~ Inclusion/exclusion checks
- ~ Pregnancy or FSH and oestradiol levels (as appropriate)
- ~ ECOG PS
- ~ Vital signs
- ~ Physical examination
- ~ Clinical chemistry
- ~ Hematology
- ~ Coagulation
- ~ Urinalysis

- ~ Thyroid function tests
- ~ Echocardiogram (or MUGA)
- ~ ECG (triplicate tests)
- ~ Tumor imaging
- ~ Disease Assessment
- ~ Tumor biopsy (fresh tissue mandatory; archival optional)
- ~ Biomarkers
- ~ Concomitant medication

Cycle 1, Day 1 (21 day cycle)

- ~ Vital signs
- ~ Physical examination
- ~ Clinical chemistry
- ~ Hematology
- ~ Coagulation
- ~ Urinalysis
- ~ ECG (triplicate tests; pre-dose and at 6 hours post dose)
- ~ Biomarkers (if not collected at Screening)
- ~ Pembrolizumab 200 mg fixed dose - infusion
- ~ BGB324 oral dosing 400 mg
- ~ PK sampling - BGB324 pre-dose, 2, 4, 6 and 8 hours post dose
- ~ PK sampling for storage - pembrolizumab (pre-dose)
- ~ Adverse events
- ~ Concomitant medication

Cycle 1, Day 2

- ~ Vital signs
- ~ Physical examination
- ~ Clinical chemistry
- ~ Hematology
- ~ ECG (triplicate test; pre-dose)
- ~ BGB324 oral dosing 400 mg
- ~ PK sampling - BGB324 (pre-dose)
- ~ PK sampling for storage - pembrolizumab (pre-dose)
- ~ Adverse events
- ~ Concomitant medication

Cycle 1, Day 3

- ~ Vital signs
- ~ Physical examination
- ~ Clinical chemistry
- ~ Hematology

- ~ ECG (triplicate test pre-dose)
- ~ BGB324 oral dosing 400 mg
- ~ PK sampling - BGB324 pre-dose, 2, 4, 6, 8 hours post dose.
- ~ PK sampling for storage – pembrolizumab (pre-dose)
- ~ Adverse events
- ~ Concomitant medication

#### Cycle 1, Day 4

- ~ Vital signs
- ~ Physical examination
- ~ Clinical chemistry
- ~ Hematology
- ~ ECG (triplicate test; pre-dose)
- ~ Biomarkers
- ~ BGB324 oral dosing 200 mg (consecutive daily dosing 21 day cycle)
- ~ PK sampling - BGB324 (pre-dose)
- ~ PK sampling for storage – pembrolizumab (pre-dose)
- ~ Adverse events
- ~ Concomitant medication

#### Cycle 1, Day 8

- ~ Vital signs
- ~ Physical examination
- ~ Clinical chemistry
- ~ Hematology
- ~ Coagulation
- ~ Urinalysis
- ~ ECG (triplicate test; pre-dose)
- ~ Biomarkers
- ~ BGB324 oral dosing 200 mg (consecutive daily dosing 21 day cycle)
- ~ PK sampling - BGB324 (pre dose)
- ~ PK sampling for storage (pre-dose) - pembrolizumab
- ~ Adverse events
- ~ Concomitant medication

#### Cycle 1, Day 15

- ~ Vital signs

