## 6.10 Prohibited Concomitant Medications Whilst Receiving Pembrolizumab

Patients are prohibited from receiving the following therapies during the Screening and Treatment period (including retreatment for post-complete response relapse) of this trial:

- Antineoplastic systemic chemotherapy or biological therapy
- Immunotherapy not specified in this protocol
- Chemotherapy not specified in this protocol
- Investigational agents other than BGB324 and pembrolizumab
- Radiation therapy
  - Note: Radiation therapy to a symptomatic solitary lesion or to the brain may be considered on an exceptional case by case basis after consultation with Sponsor.

The patient must have clear measurable disease outside the radiated field. Administration of palliative radiation therapy will be considered clinical progression for the purposes of determining PFS. *Note: Treatment with pembrolizumab and BGB324 must have been discontinued at least one week prior to radiotherapy and should not be restarted within one week of completing radiotherapy.*

- Live vaccines within 30 days prior to the first dose of trial treatment and while participating in the trial. Examples of live vaccines include, but are not limited to, the following: measles, mumps, rubella, chicken pox, yellow fever, rabies, BCG, and typhoid (oral) vaccine. Seasonal influenza vaccines for injection are generally killed virus vaccines and are allowed. However, intranasal influenza vaccines (e.g. Flu - Mist®) are live attenuated vaccines, and are not allowed.
- Systemic glucocorticoids for any purpose other than to modulate symptoms from an event of clinical interest of suspected immunologic etiology. If a patient requires physiologic doses of corticosteroids, they must discontinue their BGB324.
  - Note: Inhaled steroids are allowed for management of asthma.

Patients who, in the assessment by the investigator, require the use of any of the aforementioned treatments for clinical management should be removed from the trial. Patients may receive other medications that the investigator deems to be medically necessary.

The Exclusion Criteria describes other medications that are prohibited in this trial.

There are no prohibited therapies during the Follow Up period once the patient has discontinued both treatments.

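### The pre-treatment blood-biomarker sample is by default a Screening draw at no fixed interval from prior therapy; a Day 1 pre-dose sample should be required in every patient

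*Protocol*

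**What the plan says.** Four places in the protocol set the timing of the pre-treatment blood-biomarker sample.

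- **Footnote 9 to Tables 4 and 5:** "Blood samples will be collected at Screening (or D1 pre-dose), D4, D8, then at every study visit up to and including C9 D1".
- **Section 5.1.1, Cycle 1 Day 1 list:** "Biomarkers (if not collected at Screening"; Day 1 is therefore the fallback.
- **Table 4:** a full mark at Screening and a bracketed mark at Day 1. The general instructions explain a bracketed mark as optional, not taken every cycle, or only if applicable.
- **Synopsis, Study Procedures and Assessments:** "Blood sampling for PBMC and Axl signaling and inhibition biomarker analysis will be performed at Screening, Cycle 1, Days 4 and 8", with no mention of Day 1.

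The Screening window in Section 5.1.1 is headed "Screening (up to 28 days prior to Day 1".

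Three rules govern prior and concurrent therapy.

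- **Exclusion 11** applies to a patient who "Has had prior chemotherapy, targeted small molecule therapy, or radiation therapy within 2 weeks prior to study Day 1".
- **Exclusion 15** applies to a patient who "is receiving systemic steroid therapy or any other form of immunosuppressive therapy within 7 days prior to the first dose of study treatment".
- **Section 6.10** states: "Patients are prohibited from receiving the following therapies during the Screening and Treatment period". Its list includes chemotherapy and, outside immune-type events of clinical interest, systemic glucocorticoids.

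Section 5.3.12 names the blood markers: T-cell populations, pAxl, ERK/pERK, Akt/pAkt and others. Section 8.4 restricts the biomarker set to patients with baseline and post-baseline values but does not say which sample is the baseline. Section 8.13.1 leaves the biomarker analysis to a separate plan.

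**The concern.** The exploratory objective looks in blood for evidence of immune modulation and Axl signaling. The earliest on-treatment samples are on Days 4 and 8, so their reading depends on the one sample drawn before treatment.

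That sample has two weaknesses. Its timing is not uniform: one patient may have it four weeks before dosing and another on the morning of Day 1. It also has no minimum distance from prior therapy, because the wash-outs protect Day 1 and not the day of the draw. A patient sampled soon after chemotherapy or steroids may still be recovering when treatment starts. With one arm, no control group shows how much of a later change is recovery.

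The protocol fixes which samples are drawn. A later analysis plan can define baseline or adjust for time since prior therapy, but it cannot create a Day 1 sample that was never taken.

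**Working it through.** No figure in the protocol rests on this point, so there is none to reproduce. The check is day arithmetic, followed by an illustration.

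**Inputs.** Screening window 28 days (Section 5.1.1). Wash-out for chemotherapy, small molecules and radiotherapy 14 days (exclusion 11). Wash-out for systemic steroids and immunosuppressants 7 days (exclusion 15). First on-treatment samples on Days 4 and 8 (footnote 9).

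**Step 1: interval from the pre-treatment draw to the first on-treatment samples.**

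| Draw | To Day 4 | To Day 8 |
|---|---|---|
| 28 days before Day 1 | 28 + 3 = 31 days | 28 + 7 = 35 days |
| Day 1 pre-dose | 3 days | 7 days |

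Both rows are permitted, so the interval to Day 4 can range from 3 to 31 days between patients.

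**Step 2: distance from prior therapy, exclusion criteria alone.** The earliest Screening draw could precede the last permitted chemotherapy by up to about 28 − 14 = 14 days, and the last permitted steroid by up to about 28 − 7 = 21 days.

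**Step 3: the same with Section 6.10 applied.** Chemotherapy and systemic steroids must have ended before Screening began, so the draw should not precede them. It can still follow closely. Suppose the last chemotherapy is 15 days before Day 1, and Screening opens with the blood draw 14 days before Day 1. Exclusion 11 and Section 6.10 are both met. The sample is then 1 day after chemotherapy, with 14 days of recovery before the first dose and 14 + 3 = 17 days before the Day 4 sample. For steroids, a last dose 8 days before Day 1 and a draw 7 days before Day 1 leave 7 days of recovery before the first dose.

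**Step 4: with a Day 1 pre-dose baseline.** The gap from baseline to first dose is zero. The sample lies at least 14 days after chemotherapy, small molecules or radiotherapy, and at least 7 days after systemic steroids.

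**Step 5: illustration of size (assumed values).** Let a marker be depressed by a fraction s at the draw and fully recovered by Day 1, with no drug effect. The apparent change from baseline is 1/(1 − s) − 1.

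- s = 10%: 1/0.90 − 1 = +11%
- s = 20%: 1/0.80 − 1 = +25%
- s = 30%: 1/0.70 − 1 = +43%

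For a T-cell count this could pass for stimulation. For a signaling marker that the drug is expected to lower, it works the other way. If the drug lowers the marker by a fraction d, the observed ratio to baseline is (1 − d)/(1 − s). With d = s = 20% it is 0.80/0.80 = 1, and a real fall is hidden. The protocol gives no value for s or d.

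**Step 6: Day 15.** Footnote 9 and the synopsis ask for a sample at every study visit after Day 8, up to Cycle 9 Day 1, and the synopsis counts Day 15 as a study visit. The Day 15 list in Section 5.1.1 has no biomarker entry, and Table 4 appears blank in that column. This does not bear on the baseline, but it sits in the same lines of text.

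**The case against.** The strongest reply has four parts.

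1. **The footnote already allows a Day 1 sample, and no passage names the Screening draw as the analysis baseline.** True. A reader might infer that Screening is always the baseline; it is only the default, and the defect is a pre-treatment sample whose timing varies.

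2. **Section 6.10 bars chemotherapy and most systemic steroid use during Screening.** This stands. A reader of exclusions 11 and 15 alone might infer that the sample can precede the last chemotherapy or steroid. The wording of Section 6.10 contradicts that, although its heading speaks of the time on pembrolizumab. What remains is a sample soon after such therapy.

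3. **Baseline and adjustment belong in the separate biomarker plan, and the footnote refers to the Laboratory Manual for time-points.** Neither is shown. A reader might infer that the sponsor will read recovery as drug effect, but no such analysis is stated, so this is a risk only. The reply does not reach the collection itself: with at most 56 patients, modelling time since therapy is a weak substitute for a sample at the right time.

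4. **Eligibility limits gross suppression.** Inclusion 10 requires adequate counts at Screening and again within 10 days of treatment, inclusion 12 requires chemotherapy toxicity to have resolved to Grade 1 or less, and exclusion 14 generally bars growth factors and transfusions for 4 weeks. These narrow the problem but do not govern T-cell subsets or PBMC signaling. That recent chemotherapy or steroids alter those markers is plausible; the protocol does not establish it.

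**Conclusion.** The point holds as a cheap improvement to an exploratory objective. By default the only pre-treatment blood-biomarker sample comes from Screening, at a time that varies between patients by up to 28 days and with no minimum interval from prior therapy. In one arm, recovery after that draw may be confused with a drug effect on T-cell markers, or may mask or distort a change in signaling markers.

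A reader might go further and infer that recovery would imitate Axl inhibition. The upward recovery illustrated above does not support that: it would hide a fall in pAxl or downstream signaling.

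The size is unknown. It depends on how close the draw falls to prior therapy, which the protocol does not limit, and on how far the markers are altered, which is assumed here. The primary response-rate analysis, power and type I error are untouched. The described Data Review Committee decisions rest on safety and dosing data, response rate, duration of response and PFS, not on blood biomarkers.

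**What to change.** In footnote 9, Table 4, the synopsis and Section 5.1.1, require the blood-biomarker sample at Cycle 1 Day 1 pre-dose in every patient and name it the baseline. Align the Laboratory Manual. Recording the time from last prior therapy to the sample would help interpret what remains.

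The sponsor has to choose what happens to the Screening draw.

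- **Move it to Day 1.** The number of samples stays the same, but there is no earlier back-up if the Day 1 sample fails.
- **Keep it as a back-up.** It must then be drawn in advance in everyone, at the cost of one extra blood tube per patient.

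Either way PBMC handling falls on a busy visit, though blood is already drawn pre-dose on Day 1 for pharmacokinetics. Section 5.3.9 already combines Screening and pre-dose Day 1 values for the ECG, so a Day 1 baseline measurement has a precedent here.

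In the same edit, state whether a Day 15 biomarker sample is taken, and make footnote 9, the synopsis, Table 4 and the Section 5.1.1 list agree.

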## LIST OF ABBREVIATIONS

AE	Adverse event
ALK	anaplastic lymphoma kinase
ALT	Alanine aminotransferase
AML	Acute myeloid leukemia
ANC	Absolute neutrophil count
aPTT	Activated Partial Thromboplastin Time
AST	Aspartate aminotransferase
ATC	Anatomical Therapeutic Chemical
AUC	Area under the curve
AUC 0-∞	AUC from time zero to infinity
AUC 0-24h	AUC from time zero to 24 hours
AUC 0-48h	AUC from time zero to 48 hours
AUC 0-T	AUC from time zero to time t
BP	Blood pressure
BPM	Beats per minute
C av	average concentration
CI	Confidence interval
CIOMS	Council for International Organizations of Medical Sciences
C max	Maximum concentration achieved
CNS	Central nervous system
CR	Complete response
CRF	Case report form
CRO	Contract Research Organization
CSR	Clinical study report
CT	Computed tomography
CTCAE	Common Terminology Criteria for Adverse Events
CV	Cardiovascular
DCR	Disease control rate
DLT	Dose limiting toxicity
DoR	Duration of response
DSUR	Development Safety Update Report
EC	European Community
EC	Ethics committee
ECG	Electrocardiogram
ECI	Events of clinical interest
ECOG	Eastern Cooperative Oncology Group
eCRF	Electronic Case Report Form
EGFR	Epidermal growth factor receptor
EMT	Epithelial-to-mesenchymal transition
EU	European Union

FDA	Food and Drug Administration
FPI	First patient in
FPPE	Formalin fixed paraffin embedded
FSH	Follicle-stimulating hormone
FT3	Free Triiodothyromine
GCP	Good Clinical Practice
G-CSF	granulocyte-colony stimulating factor
GM-CSF	Granulocyte-macrophage colony-stimulating factor
GMP	Good Manufacturing Practice
HCV	Hepatitis C virus
hERG	Human ether-à-go-go related gene
HIV	Human immunodeficiency virus
HPMC	Hydroxypropyl methylcellulose
hr	Hour
i.v.	Intravenous(ly)
IB	Investigator's Brochure
ICF	Informed consent form
ICH	International Conference on Harmonization
IEC	Institutional Ethics Committee
IHC	Immunohistochemistry
IMP	Investigational medicinal product
IND	Investigational new drug
INR	International normalization ratio
IRB	Institutional Review Board
IUD	Intrauterine device
LPLV	Last patient, last visit
mAb	Monoclonal antibody
MDS	Myelodysplastic syndrome
MRI	Magnetic resonance imaging
MTD	Maximum tolerated dose
MUGA	Multi Gated Acquisition Scan
NCI CTCAE	National Cancer Institute Common Terminology Criteria for Adverse Events
NYHA	New York Heart Association
ORR	Objective response rate
OS	Overall survival
PBMC	Peripheral blood mononuclear cell(s)
PD	Pharmacodynamic(s)
PFS	Progression-free survival
PIS	Patient information sheet
PK	Pharmacokinetic
PT	Prothrombin time
PTT	Partial Thromboplastin Time

Q2W	(dose) every 2 weeks
Q3W	(dose) every 3 weeks
Qd	(dose) daily
qPCR	quantitative polymerase chain reaction
QTc	QT interval corrected for heart rate
QTcF	QT interval utilizing Fridericia's correction
RNA	Ribonucleic acid
RP2D	Recommended Phase 2 dose
RTK	receptor tyrosine kinases
SAE	Serious adverse event
SAP	Statistical Analysis Plan
SmPC	summary of product characteristics
SUSAR	Suspected unexpected serious adverse reaction
$t_{1/2}$	Elimination half-life
T3	Triiodothyromine
TL	Target lesion
$t_{max}$	Time to maximum concentration
TMF	Trial Master File
TPS	tumor proportion score
TSH	Thyroid stimulating hormone
ULN	Upper limit of normal
US	United States (of America)
DRC	Data Review Committee
TNBC	Triple negative breast cancer
TN-IBC	Triple negative inflammatory breast cancer
FISH	Fluorescent in situ hybridization
CISH	Chromogenic in situ hybridization
LDH	Lactate Dehydrogenase
EDC	Electronic Data collection
PD	Progression of disease
CrCl	Creatinine clearance

